6.2 PREPARATION/HANDLING/STORAGE/ACCOUNTABILITY

6.2.1 ACQUISITION AND ACCOUNTABILITY

Sirolimus capsules (2 mg) and matching placebo will be acquired in randomized per patient bottles from the Town Total Compounding Pharmacy and delivered to the study coordinator/ PI for dispensing to subjects

Town TOTAL Compounding Center
[name]
[name]
[contact]

The Town Total Compounding Center pharmacy will randomize, store and dispense study drug to our center.

The study coordinator will maintain drug accountability with a drug accountability log.

6.2.2 FORMULATION, APPEARANCE, PACKAGING, AND LABELING

Sirolimus capsules (2 mg) and matching placebo capsules will be packaged in tight, light-resistant bottles as defined in the US Pharmacopeia. Sufficient bottles for 3 months of study will be packed for each participant, taking into consideration the potential increases in sirolimus dose after measuring sirolimus levels in blood. Each bottle label will bear the site number, investigator's name, participant number and the bottle number which comprises the participant number followed by a sequential number (01, 02, 03, 04, etc.).

The label on the bottles will include a fixed information section (to include the product name, storage conditions, instructions etc.) and variable information section. The variable information section will include 3 parts: 2 detachable parts, which will be attached to the participant's file upon bottle dispensing and 1 part to remain on the bottle. The variable information section will include the following variable data: site number, investigator name, participant number, bottle number, batch code and expiration date (all to be pre-printed on the label) and blank field for visit number to be manually filled in by the Investigator or designee upon provision of bottle to the participant.

Study drug supplies will be kept at the Total Town Compounding pharmacy, in a secure, limited-access, temperature/humidity-controlled area and a temperature/humidity log will be maintained. Only authorized personnel will have access to the study drug. The Total Town Compounding pharmacy personnel will be responsible for correct storage and handling of the study drug. The study drug bottles will be dispensed to the participant at the study site at each study visit starting at baseline visit (except for termination visit). The site number and investigator's name will be pre-printed on the bottle label. Since the participant number is pre-printed on the bottle label, assigning the right bottles to the

participants is straightforward. After assigning a bottle to the participant, the site personnel should fill in the visit number on the label of the dispensed bottle as well as on the detachable parts that would be attached to the participant's file.

At each dispensing visit, the participant will be dispensed with the study drug with the participant's number printed on the label. Any of the bottles designated for a participant can be dispensed in each of the dispensing visits. The bottle with the bottle number "participant # -R" is designated to replace damaged or lost bottles and should be used only for replacement.

In case a replacement bottle is required, the Total Town compounding pharmacist will be notified.

Participants will be instructed to return all used empty bottles and unused study drug at each visit.

The study coordinator is responsible for performing study drug accountability at the site and the accountability of the returned study drug.

6.2.3 PRODUCT STORAGE AND STABILITY

Capsules will be stored at 20°C to 25°C (US Pharmacopeia Controlled Room Temperature) (68°F - 77°F). If the study drug supplies appear to be damaged/missing upon arrival at the NYU Dysautonomia Center, the study manager should be contacted immediately. Each shipment of study drug supplies for the study will contain a shipment form describing the content of shipment. This form will assist in maintaining current and accurate inventory records. When a shipment is received, the NYU Dysautonomia Center will acknowledge receipt of the study drug supply by signing the acknowledgment of receipt section.

6.3 MEASURES TO MINIMIZE BIAS: RANDOMIZATION AND BLINDING

After a participant meets the eligibility criteria, During the baseline visit, participants will be allocated to a treatment group, based on a randomization procedure employing a 3:1 assignment ratio, and a scheme using blocks stratified by MSA type (cerebellar or parkinsonian) and sex. The randomization sequence will be performed by the independent medical monitor (IMM) and delivered, in a closed envelope, to the Total Town compounding pharmacy. The compounding pharmacist will use the randomization order to send the proper medication to the study coordinator. The patient will be then instructed to take one capsule (i.e., 2 mg of sirolimus or matching placebo) daily and have sirolimus levels in blood at specific times throughout the study. Depending on the sirolimus levels, the sirolimus dose may be increased or decreased throughout the duration of the study.

A participant ID will be assigned by the center and kept in a written log. The participant IDs will be used to code the data obtained during the study visits, including brain MRI, OCT, and blood for exosomes. The participant IDs will follow the following format: three letters followed by three numbers (i.e., NYU001). The three letters correspond to center (i.e., New York University).

Drug Kit numbers will be assigned by the pharmacy and provided to the statistician who will then assign to the randomization block scheme. There will be an electronic validation of the participant's eligibility. If they are found to be eligible the system will send the drug kit number based on the known randomization sequence to the coordinator via electronic format. The drug kit number will also be used

by the pharmacist to send the proper medication. The Drug Kit number will not replace the Participant ID.

Study drug will be stored and dispensed by the study PI or research nurses delegated by the PI, located at:

NYULMC
[name]
[name]
[name]

Blinding

The participant, as well as investigators and any personnel involved in the participant's recruitment, assessment, monitoring, analysis and data management, will be blinded to the participant's treatment assignment.

The only personnel unblinded to the intervention will be the compounding pharmacist, the independent medical monitor (IMM), the independent pharmacist (independent from the compounding pharmacy and any other study members) for the purposes of sirolimus therapeutic levels monitoring. The independent pharmacist will maintain the blinding of the sirolimus levels and dose escalation during the clinical trial by making dosing recommendations for those patients receiving active agent, and by generating a sham therapeutic drug level for those patients receiving placebo. The independent study pharmacist will then make dosing recommendations to maintain sirolimus trough levels between 5 and 20 ng per milliliter in those patients taking active agent, as well as corresponding sham dose adjustments in patients taking placebo, in order to maintain investigator and subject blinding during the clinical trial.

Sirolimus therapeutic levels monitoring

An independent pharmacist will remain unblinded to each patient allocation and to the sirolimus blood level of each patient to allow the adjustment of such levels. The independent pharmacist will generate a simulated/sham value for patients receiving placebo in order to maintain the blinding of the investigators and the patients (66).

Emergency Unblinding

Unblinding of the participant's drug assignment will occur under any of the following circumstances:

1. Pregnancy.
2. Serious adverse event when the study drug assignment is required to make treatment decisions for the individual participant.
3. Death of participant when the death has been considered to be probably or possibly related to the study drug.
4. Death of participant when the relationship to study drug has been undetermined (e.g., after multiple efforts, the investigator team was unable to obtain medical records and/or death certificate).
5. Other circumstances that, under the opinion of the PI or the overseeing agencies, require emergency unblinding.

Unblinding of the participant's drug assignment will be done by the compounding pharmacist, the independent medical monitor, or the independent pharmacist, after the PI request. The IRB should be notified of the event prior to breaking of the code, if possible. If this is not possible, the IRB should be notified immediately afterwards, and the participant's drug assignment should be revealed. The circumstances leading to the breaking of the code should be fully documented, in the investigator's study files and in the participant's source documentation. The independent medical monitor and the compounding pharmacist will maintain the randomization lists and will be available to break the blind in the event of an emergency. A randomization list will be sent to the compounding pharmacist at the beginning of the study. A backup copy of the complete set of randomization assignments will also be given to the IMM and the PIs in a sealed envelope. We do not anticipate that it will ever be necessary that the PI will have to open this envelope during the trial. We will carefully document the reasons for any emergency unblinding should it ever become necessary to do this.

6.4 STUDY INTERVENTION COMPLIANCE

At each study visit, the investigator/site coordinator will assess the participant's compliance with the prescribed regimen for the study medication. This will include checks of protocol compliance and use of study drug in order to assess the reliability of participant-generated data. Participants who fail to comply with the study requirements may be withdrawn from the study, following consultation with the PI.

Compliance with the dosing regimen will be determined by performing study drug accountability of returned capsules and bottles of the study drug used and unused. The number of used, unused and lost capsules will be recorded on the CRF by the study coordinator.

Participants with less than 75% overall compliance during the entire study will be considered non-compliant. These participants will be included in the intention to treat analysis set and complete analysis set as defined in sections 12.3.1 and 12.3.2 respectively. However, these participants will be excluded as in the per-protocol analysis set.

Accountability records must be maintained at the site at all times. Accountability of the returned study drug should be performed and recorded at the site by the study coordinator. The participant number, the date, batch code, bottle number and quantity of study drug returned by the participant will be checked for correctness and recorded on the appropriate accountability forms.

6.5 CONCOMITANT THERAPY

Prohibited medications

- Intravenous immunoglobulin within 3 months prior to baseline visit
- Rituximab within 3 months prior to baseline visit
- Oral or intravenous corticosteroids within 3 months prior to baseline visit (topical or inhaled corticosteroids are allowable)
- Cyclosporine within 3 months prior to baseline visit
- Methotrexate within 3 months prior to baseline visit
- Azathioprine, mycophenolate or any other immunosuppressants or immunomodulatory drugs within 3 months prior to baseline visit
- Any anti-neoplastic or immunomodulatory agent including but not limited to nilotinib,

- natalizumab, infliximab and bevacizumab within 3 months prior to baseline visit
- Any other investigational drug within 3 months prior to baseline visit

Allowed medications

- All anti-parkinsonian medications including but not limited to L-dopa, rasagiline, selegiline, amantadine.
- Fludrocortisone, pyridostigmine and vasopressin and analogs.
- Beta-blockers
- ACE inhibitors
- Alpha adrenergic agonists including but not limited to midodrine
- Norepinephrine precursors including but not limited to droxidopa
- Norepinephrine reuptake inhibitors including but not limited to atomoxetine or venlafaxine
- Serotonin reuptake inhibitors and other antidepressants
- Benzodiazepines
- Baclofen
- CoQ10
- Metformin and other anti-diabetic medications
- Topical or inhaled corticosteroids
- Non-steroidal anti-inflammatory drugs
- Topical anesthetic (e.g., lidocaine patch, lidocaine mouthwash)
- Statins
- Bile sequestrants
- Fibrates
- Trimethoprim/sulfamethoxazole
- Clindamycin
- Primaquine

Efforts will be made to maintain medications and dosages stable until the final study visit.

Standard non-pharmacologic measures to treat orthostatic hypotension are encouraged. These include the use of elastic stockings/abdominal binder, elevation of the head of the bed, increased fluid intake, and liberal salt intake. The participant is encouraged to maintain stable conditions of these measures.

Disallowed concomitant medications during the study:

- Treatment with inhibitors of CYP3A4 (which may decrease the metabolism of sirolimus and increase sirolimus levels) within 1 month prior to baseline visit: nifedipine, verapamil, clotrimazole, fluconazole, itraconazole, clarithromycin, erythromycin, troleandomycin, cisapride, metoclopramide, bromocriptine, cimetidine, danazol, HIV-protease inhibitors (e.g., ritonavir, indinavir); grapefruit.
- Treatment with inducers of CYP3A4 (which may increase the metabolism of sirolimus and decrease sirolimus levels) within 1 month prior to baseline visit: carbamazepine, phenobarbital, phenytoin, rifabutin, rifampin.

6.5.1 RESCUE MEDICINE

Not applicable

7 STUDY INTERVENTION DISCONTINUATION AND PARTICIPANT DISCONTINUATION/WITHDRAWAL

7.1 DISCONTINUATION OF STUDY INTERVENTION

Discontinuation from study drug does not mean discontinuation from the study, and remaining study procedures should be completed as indicated by the study protocol. If a clinically significant finding is identified (including, but not limited to changes from baseline) after enrollment, the investigator or qualified designee will determine if any change in participant management is needed. Any new clinically relevant finding will be reported as an adverse event (AE).

The data to be collected at the time of study intervention discontinuation will include the following:

- EKG
- Concomitant medications
- Physical examination
- Vitals signs
- CBC, CMP, CPK, urinalysis
- 24-hour urine collection
- Lipid panel
- Sirolimus levels in blood
- Retrieve study medication
- Recording of AE
- UMSARS scale

7.2 PARTICIPANT DISCONTINUATION/WITHDRAWAL FROM THE STUDY

Participants are free to withdraw from participation in the study at any time upon request. An investigator may discontinue or withdraw a participant from the study for the following reasons:

- Pregnancy
- Significant study intervention non-compliance
- If any clinical adverse event (AE), laboratory abnormality, or other medical condition or situation occurs such that continued participation in the study would not be in the best interest of the participant
- Disease progression which, in the opinion of the investigator, requires discontinuation of the study intervention
- If the participant meets an exclusion criterion (either newly developed or not previously recognized) that precludes further study participation
- Participant unable to receive study drug for 15 days or more.

The reason for participant discontinuation or withdrawal from the study will be recorded on the electronic Case Report Form (CRF). Subjects who sign the informed consent form and are randomized but do not receive the study intervention may be replaced. Subjects who sign the informed consent form, and are randomized and receive the study intervention, and subsequently withdraw, or are withdrawn or discontinued from the study, will not be replaced.

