- CBC, CMP, CPK (8 ml of blood) and urinalysis with 24-hour urine collection
- Lipid panel (2 ml of blood)
- Sirolimus levels in blood (5 ml of blood)
- Adverse event reporting

In case the safety lab assessments are performed locally (e.g., at a local laboratory near the subjects' home), the PI or a licensed research member of the team will provide the patient with a prescription for the required tests. A research nurse, investigator or study manager will perform a phone call to assess adverse events within 7 days of the study visit.

To account for delays during the first month of treatment, Visit 7 (2-month) may be skipped to ensure that Visit 8 occurs 3 months (+/- 15 days) after the initiation of the study drug.

To maintain the blinding, the results of the sirolimus levels in blood will remain blinded to the investigators and study coordinators and delivered to the independent pharmacist in charge of determining if the sirolimus dosage should be increased or decreased.

End of study visit/early termination: the following tasks/procedures will be performed at the clinic during the termination visit (Study Visit 17):

- EKG
- MoCA
- Concomitant medications
- Physical examination
- Vitals signs
- CBC, CMP, CPK (8 ml of blood) and urinalysis with 24-hour urine collection
- Lipid panel (2 ml of blood)
- Sirolimus levels in blood (5 ml of blood)
- Retrieve study medication
- Recording of AE
- UMSARS scale
- Blood sample for exosomes (2 ml of blood)
- Retinal optical coherence tomography
- Brain MRI

We will accept a visit window of 15 days before or after the target date of this visit.

The reason for discontinuation of therapy will be documented in the source documents and captured on the CRF. In the event that the study drug is discontinued early, an early termination visit should be

completed as close to the last dose date as possible. Participants will be followed for the duration of 12 months.

If a participant is withdrawn because of an adverse event, the appropriate “Withdrawal Section” of the CRFs should be fully completed in addition to the Adverse Event module. The Independent Medical Monitor should be informed of all participants who are withdrawn for this reason. Participants will be followed for 12 months.

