- If sirolimus levels are < 5 ng/mL, the participant will be instructed to take sirolimus 2 mg two capsules daily (4 mg total dose) or matching placebo; sirolimus levels will be then measured again 7 days after the patient began taking 4 mg/day (+ 3 days). If sirolimus levels are between 5 and 20 ng/ml, the subject will continue with that dose until the next measurement of sirolimus levels on Visit (+ 3 days).
- If sirolimus levels are > 30 ng/ml with one capsule/day, the subject will be excluded from the trial due to the high risk of adverse events.

Subjects who were instructed to increase their dose to 4 mg will undergo another measurement of sirolimus levels 7 days after the previous dose adjustment (+ 3 days):

- If sirolimus levels are < 5 ng/mL, the participant will be instructed to increase sirolimus to 2 mg three capsules daily (6 mg total dose) or matching placebo. Sirolimus levels will be then measured 7 days after the patient began taking 6 mg/day (+ 3 days).
- If sirolimus levels are between 5 and 20 ng/ml, the subject will continue with that dose until the next measurement of sirolimus. If the sirolimus levels are > 20 ng/ml, the subject will be instructed to go back to the 2 mg/day dose and continue with that dose until the next measurement of sirolimus levels.

From Visit 3 to Visit 6, sirolimus level blood draw will take place 7 days (+3 days) after the previous dose adjustment has taken place (i.e., 7 days after the patient started taking the adjusted dose).

From Visit 7 onwards, subjects will be instructed to increase or decrease their sirolimus dose (between a min dose of 2 mg/day to a max dose of 6 mg/day) depending on blood levels (target: 5-20 ng/ml) and the emergence of adverse events.

Expected dose-limiting effects requiring sirolimus dose reduction are:

- Grade 2 stomatitis or mucositis
- Grade 2 lymphedema
- Grade 2 proteinuria
- Grade 2 renal failure
- Grade 3 pneumonitis
- Grade 2 diarrhea

Every attempt will be made to maintain the participant on the full dose. If the participant is unable to maintain the full dose, the minimum acceptable dose is 2 mg once a day. An attempt will be made to increase the dose with a re-challenge at a later date. Capsules should be swallowed whole with a glass of water or may be taken with food to minimize gastrointestinal side effects.

To maintain investigator and subject blinding during the clinical trial, the results of the sirolimus

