9.2 SAMPLE SIZE DETERMINATION

This study is a randomized, double blind placebo-controlled futility trial in which the primary outcome measure value (UMSARS total score) in a cohort of patients with MSA taking active agent will be compared to a known value from historical controls previously published in the literature. The primary outcome measure was used to calculate the sample size.

The primary statistical analysis will involve a comparison of the mean absolute difference in the active sirolimus group with a pre-specified fixed value, constituting a 4-point reduction in the expected mean increase in the UMSARS total score over 48 weeks without treatment. The expected mean increase in total UMSARS outcomes were obtained from the *U.S. Natural History Study of MSA* (n=96) (39), that reported that the total UMSARS score at 12 months increased a mean of 7.5 (SD: 8.4) absolute points from baseline. Also data from a phase III double-blind placebo-controlled 12-month clinical trial with rifampicin in MSA performed in the U.S. (40) (which was found to be ineffective to slow the progression of the disease) showed that in patients taking placebo (n=50) the total UMSARS score at 12 months increased a mean of 10.8 (SD: 10.7) absolute points from baseline. A weighted analysis of these two populations showed the pooled total UMSARS score at 12-months in patients with MSA in large studies performed in the U.S. had increased a mean of 8.6 (SD: 9.2) points from baseline.

Also, recent studies (38) have determined that the minimally clinically important difference (MCID) in the total UMSARS score is 3.5 points after 48-weeks from baseline.

Taking into consideration this MCID, for this trial, we will assume a promising difference in the UMSARS total score of 4 points between those taking active agent and the historical controls. Specifically, our null hypothesis is that patients receiving sirolimus will have a UMSARS total score progression of only 4.6 points at week 48 higher than baseline, compared to a progression of 8.6 points at week 48 from baseline reported in historical controls from natural history studies and placebo-controlled trials of MSA. Our alternate hypothesis is that sirolimus will be futile to slow the progression of the disease in patients with MSA. The statistical definitions are as follows:

$H_0: \theta_E - \theta_p \leq 4$ where $\theta_p = 8.6$ points increase at week 48 from baseline described in historical controls

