$H_0: \theta_E \leq 4.6$ points increase at week 48 from baseline

$H_1: \theta_E > 4.6$ points increase at week 48 from baseline

Therefore, assuming an alpha of 0.05, and a power of 0.8 (one sided, as patients with MSA have not been reported to improve spontaneously) to detect a progression of 4.6 points (i.e., 8.6 minus 4) in the UMSARS total score after 48-weeks from baseline we will need to enroll 38 patients in the active agent arm. Anticipating a 10% for dropouts rate, we will need to enroll 42 patients in the active agent arm.

This trial will include a placebo group to facilitate blinding in a 3:1 proportion. However, statistical comparisons for the primary and secondary efficacy outcome measures will be performed between the active agent arm and the historical controls. We will therefore enroll 14 patients in the placebo arm.

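### Section 7.2 permits withdrawal from the study for reasons that amount to being off drug, so week-48 UMSARS can be lost from faster progressors, biasing the result towards non-futility

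*Combined protocol and SAP*

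**What the plan says.** Section 7.1 is clear: "Discontinuation from study drug does not mean discontinuation from the study", and the remaining procedures should still be done. It also lists a UMSARS among the data taken when drug is stopped. Section 4.1, on early drug discontinuation, says "Participants will be followed for the duration of 12 months", and repeats the 12-month follow-up for participants withdrawn because of an adverse event.

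Section 7.2 concerns withdrawal from the study. Among the reasons for which an investigator may withdraw someone are significant non-compliance, "Participant unable to receive study drug for 15 days or more" and "Disease progression which, in the opinion of the investigator, requires discontinuation of the study intervention". Participants who have been treated and then leave are not replaced.

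Section 6.1.2 says that, when the sirolimus level is above 30 ng/ml on one capsule a day, "the subject will be excluded from the trial due to the high risk of adverse events". Unlike 7.2, this is worded as mandatory.

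Section 9.4.2 tests the mean week-48 change in the sirolimus arm against a fixed historical value with a one-sample t-test, and plans multiple imputation for missing data. Section 4.1 says that the placebo arm is not used for the primary outcome.

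**The concern.** The progression criterion in 7.2 describes a reason to stop drug, yet it stands in a list of reasons to leave the study. Nothing says whether the week-48 UMSARS is still collected once a 7.2 criterion is applied. Section 4.1 adds to the doubt. It treats the end-of-study and early-termination visit as one visit, held close to the last dose, so staff could take the UMSARS at that visit as the final one.

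Loss through disease progression is related to the outcome. Higher UMSARS is worse, and the null hypothesis is a mean rise of 4.6 points or less, meaning the drug is promising. Losing the fastest progressors lowers the observed sirolimus mean and makes futility harder to declare. The comparator is a fixed number, so nothing in the primary comparison offsets selective loss. The protocol says that a non-futile result would strongly support a phase III trial, so the error would fall on the decision that the study exists to make.

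**Working it through.** **The plan's own figures.** The historical mean is (96 × 7.5 + 50 × 10.8)/146 = 8.63, which agrees with Section 9.2, where the pooled score "had increased a mean of 8.6 (SD: 9.2) points from baseline". The margin is 4 points ("we will assume a promising difference in the UMSARS total score of 4 points"), giving the threshold 8.6 − 4 = 4.6. The error rates are "assuming an alpha of 0.05, and a power of 0.8 (one sided").

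Sample size: n = [SD × (z₀.₉₅ + z₀.₈₀)/δ]² = [9.2 × (1.645 + 0.842)/4]² = 32.7, so 33, or 35 with the t distribution. The plan states 38, which these inputs do not reproduce. The difference is conservative (power at 38 is 0.838 by the t distribution) and the point here does not depend on it. The step to 42 matches 38 × 1.10 = 41.8, so the plan allows for 4 dropouts among 42.

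**Completers-only shift.** Assume an overall true mean of 8.6 (no drug benefit) and k of 42 leaving with true mean change c. The completers' mean is (8.6 × 42 − k × c)/(42 − k).

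| k | c | Completers' mean | Shift | Share of 4-point margin |
|---|---|---|---|---|
| 4 | 15 | (361.2 − 60)/38 = 7.93 | 0.67 | 17% |
| 4 | 20 | (361.2 − 80)/38 = 7.40 | 1.20 | 30% |
| 6 | 15 | (361.2 − 90)/36 = 7.53 | 1.07 | 27% |
| 6 | 20 | (361.2 − 120)/36 = 6.70 | 1.90 | 48% |

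The values of k and c are assumptions. Four leavers use the whole planned dropout allowance, and six exceed it.

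**Effect on the decision.** In 100,000 simulated trials, 42 sirolimus patients had normally distributed changes with true mean 8.6 and SD 9.2. Completers were tested one-sided at 0.05 against 4.6. Those lost were chosen either at random or by a tendency to leave that correlated (ρ) with a worse change. The entries are the probability of correctly declaring futility, with the average observed mean in brackets.

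| Lost of 42 | Random | ρ = 0.3 | ρ = 0.5 | ρ = 0.7 |
|---|---|---|---|---|
| 0 | 0.872 (8.61) | – | – | – |
| 4 | 0.841 (8.61) | 0.754 (8.11) | 0.696 (7.78) | 0.635 (7.45) |
| 6 | 0.822 (8.61) | 0.691 (7.91) | 0.595 (7.43) | 0.504 (6.96) |
| 8 | 0.801 (8.61) | 0.625 (7.71) | 0.498 (7.10) | 0.379 (6.50) |

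With the planned four dropouts, random loss costs about 3 percentage points of power. Outcome-related loss costs about 12 to 24 (0.872 − 0.754 to 0.872 − 0.635). The number lost and ρ are assumptions. Both tables show the bias before any imputation.

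**The case against.** **Section 4.1 and permissive wording.** Section 7.2 permits withdrawal and does not order it. Section 4.1 requires 12-month follow-up even for participants withdrawn for an adverse event, so withdrawal there does not end follow-up. Read with 7.1, this leaves 7.2 ambiguous; it does not amount to an instruction to stop collecting scores. A reader might infer that the plan removes its fastest progressors, and the text does not support that. What stands is that an opinion-based trigger tied to progression is available and that the plan does not say what happens to outcome collection when it is used. On non-compliance, Section 6.4 keeps participants below 75% compliance in the intention-to-treat set, which weakens that limb.

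**The high-level exclusion.** A reader might take 6.1.2 as further loss of those likely to do worst. Nothing links a level above 30 ng/ml to faster progression; the stated reason is adverse-event risk. The rule would normally apply at the first level check, and such participants would already fall outside the Section 9.3 set, which needs at least three months of drug. The passage needs reconciling with 7.1 and 4.1, but it is not evidence of progression-related loss.

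**Intention to treat.** It is tempting to say that 7.2 breaks the intention-to-treat claim. Section 9.3 departs from it through its own three-month requirement, which is a separate matter. Section 7.2 governs data collection.

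**Size.** The planned analysis is not completers-only. UMSARS is scheduled at months 3, 6 and 9 and taken when drug is stopped, the synopsis allows the latest available score, and multiple imputation is planned. A fast progressor who leaves will usually have an earlier score showing some decline, so the residual bias should be smaller than tabulated. This objection largely stands. Two limits remain: in a progressive disease an early score used as the week-48 value understates decline, which is the same direction of bias, and no analysis is stated for scores missing because of the outcome itself.

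**Conclusion.** The inconsistency is real. Section 7.2 permits, without requiring, withdrawal from the study for progression that leads to stopping drug, 15 days or more off drug, or non-compliance, while 7.1 and 4.1 keep such participants in follow-up. The progression criterion is plainly outcome-related. Time off drug is plausibly so, and the documents say nothing either way.

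The bias from losing fast progressors is towards non-futility. The shift of 0.7 to 1.9 points (17% to 48% of the margin) is a completers-only illustration resting on assumed numbers of leavers and assumed changes. It should not be read as the expected bias of the planned analysis, which the mitigating data and imputation would reduce by an amount not estimated here. The point merits a change of wording because the remedy is small and the primary comparison is exposed to this kind of loss.

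**What to change.** Reconcile Sections 4.1, 6.1.2, 7.1 and 7.2 so that stopping study drug is separated from ending outcome collection, leaving the clinical criteria to the clinicians. State that the UMSARS assessments already scheduled through week 48 continue after drug is stopped or a 7.2 criterion is met, unless consent is withdrawn, contact is lost, the participant dies, or the investigator judges that staying in the study is not in the participant's interest. Say that an early-termination UMSARS does not replace the week-48 one.

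For week-48 scores still missing, add a missing-not-at-random sensitivity analysis. For example, add a range of worsening shifts to the imputed sirolimus scores and report the shift at which the futility conclusion changes.

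Under Section 9.3 as written, the extra scores would enter the primary analysis only for participants with at least three months of drug.

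Cost: a protocol amendment, some extra on-site visits by off-drug participants, which may be harder for those progressing fastest, and a little more analysis. The visits are already in the schedule of activities; the documents give no budget.
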